5.2. Subject Exclusion Criteria

Subjects eligible to participate in this study must not meet any of the following exclusion criteria:

1. History of neurological symptoms or signs, or anaphylactic shock following administration of any vaccine.
2. Known or suspected (or have a high risk of developing) significant impairment/alteration of immune function (excluding that normally associated with advanced age) as judged by PI/SI.
3. Receipt of: a) Current (including within 60 days before Visit 1 or planned during the study) daily use of immunosuppressive drugs: i) systemic glucocorticoids ≥ 10 mg prednisone per day ii) cytotoxic drugs b) Investigational drugs within 30 days before, or planned during, the study c) Blood products within 3 months before, or planned during, the study d) Influenza vaccine within 6 months before the study or planned during the study e) Other vaccines within 30 days before, or planned during, the study.
4. Any serious disease such as: cancer, autoimmune disease, advanced arteriosclerotic disease or complicated diabetes mellitus, chronic obstructive pulmonary disease (COPD) that requires oxygen therapy, acute or progressive hepatic disease, acute or progressive renal disease, or congestive heart failure, as judged by the PI.
5. An acute illness, which occurred within 1 week before first vaccination, as judged by the PI/SI, or body temperature greater than: for participants age 50-59 37.9°C (axillary or

- forehead) or 38.4 °C (oral), or 38.9°C (ear/tympanic or rectal); for participants of age 60 or more greater than 37.2°C (axillary or forehead) or 37.7 °C (oral), or 38.2°C (ear/tympanic or rectal); which occurred within 1 week before first vaccination.
6. Anatomical deficiencies which exclude possibility of taking NP swab or throat and nasal swab.
 7. Women who are breastfeeding or planning pregnancy during the period of the study.
 8. Institutionalized* subjects unable to come to the study site as expected by the Protocol.
- *except for institutionalization without subsequent overnight stays

5.3. Treatment Assignment Procedures

5.3.1. Randomization Procedures

Central randomization will be implemented in this study. Subjects will be randomized to 1 of 2 treatment arms, based on a computer-generated randomization schedule prepared by or under the supervision of the sponsor before the study. The randomization will be stratified by cohort and age group (i.e., 50- 65, ≥ 65) and balanced by using permuted blocks. At least 50% of study participants will be 65 or older in each randomization cohort. The Interactive Web Response System (IWRS) will assign a unique treatment code, which will dictate the treatment assignment and matching study drug kit(s) for the subject.

For season 2, the randomization will be further stratified by sub-study participation (i.e. Yes or No).

For the CMI substudy, 350 subjects from sites participating to the sub-study (sub-study sites) are randomly chosen among 700 sub-study sites subjects with approximately 263 subjects selected at random from 350 M-001 sub-study sites subjects and approximately 87 from 350 placebo sub-study sites subjects.

Once consented and upon entry of demographic data and confirmation of eligibility for this trial, the subject will be enrolled. A total of 12,000 subjects will be randomly assigned to one of 2 arms: experimental and control. A total of 700 subjects will be randomly chosen to participate to the sub-study, with approximately 263 subjects selected at random from 350 M-001 sub-study sites subjects and approximately 87 from 350 placebo sub-study sites subjects.

The investigator will not be provided with randomization codes. The codes will be maintained within the IWRS, which has the functionality to allow the investigator to break the blind for an individual subject, if necessary.

Per International Conference on Harmonisation (ICH) guideline E6: Good Clinical Practice (GCP), screening records will be kept at each participating site to document the reason why an individual was screened, but failed trial entry criteria.

5.3.2. Masking Procedures

This is a modified double-blind study. Blinding will prevent conscious or unconscious misclassification of study endpoints based on subjective perceptions; blinding will be accomplished by using a randomization scheme for the participants.

Subjects, investigators, and study personnel performing any study-related assessments following study injection, as well as collecting swab specimens or blood samples, will be blinded to study group and treatment assignment to both: M-001 or placebo. Laboratory personnel will be blinded to treatment assignment. Separate unblinded laboratory personnel will be assigned if needed.

As the M-001 and placebo solutions differ in appearance (see section 6.1), at each study site, an appropriately qualified person, who will otherwise not be involved in the treatment or follow-up of trial patients, will not be blinded to study treatment. The person will be responsible for the preparation of the study treatment syringe. This will in most cases be the site nurse.

The site unblinded staff member will be responsible for preparing the syringe and covering it or making it (the content) in other way not visible for the subject before its administration to keep the subject blinded. This un-blinded staff member will not participate in the assessment of respiratory illnesses or ILI, or in the collection of safety information.

The Data and Safety Monitoring Board (DSMB) may receive data in aggregate and by treatment arm, or may be unblinded to individual subject treatment assignments, as needed, to adequately assess safety issues.

Refer to the relevant Unblinding Plan for unblinding procedures.

5.3.3. Reasons for Withdrawal

Subjects may voluntarily withdraw their consent for study participation at any time and for any reason, without penalty.

A subject may withdraw or be withdrawn from the study for any of the following reasons:

- Medical disease or condition, or any new clinical findings for which continued participation, in the opinion of the site PI or appropriate SI, would compromise the safety of the subject, or would interfere with the subject's successful completion of the study, or would interfere with the evaluation of responses.
- Subject no longer meets eligibility criteria.
- As deemed necessary by the site PI or appropriate SI for noncompliance or other reasons.
- Subject withdrawal of consent.
- Subject lost to follow-up.
- Termination of the study or the study cohort.
- New information becomes available that makes further participation unsafe.

Subsequent study vaccinations will not be administered to a subject if any of the following criteria are met:

- Medical condition for which continued participation, in the opinion of the site PI or appropriate SI, would pose a risk to the subject or would be likely to confound interpretation of the results.

- Presence of signs or symptoms that could confound or confuse assessment of study vaccine reactogenicity. For subjects with injection site or systemic signs or symptoms, or with an acute illness, the subsequent study vaccinations should be postponed/deferred until signs, symptoms, or acute illness have sufficiently resolved as per PI/SI judgment, and if within the expected protocol-specified window for that visit. If outside this window, the PI must first obtain approval for the second study vaccination from the study sponsor and the documentation of the approval should be filed in the subject's file.
- Any unresolved by or continuing at Visit 2 Grade 3 AE. An unresolved or continuing Grade 1 or 2 AE (grade 2 except for temperature which at grade 2 is not acceptable for vaccination) is permissible unless, in the opinion of the PI or SI, it would render study vaccination unsafe or interfere with the evaluation of responses.
- Solicited reactogenicity event grade 3 or AE grade 3 AE, within the 8 days following study vaccination (day of the vaccination inclusive), that has no alternative (to the vaccination) etiology.
- Subject no longer meets eligibility criteria.
- As deemed necessary by the site PI or appropriate SI for noncompliance or other reasons.
- Subject refusal of further study vaccination.
- Subject withdrawal of consent.
- Subject lost to follow-up.
- Termination of the study.
- New information becomes available that makes further participation unsafe.

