5.3.4. Handling of Withdrawals

The primary reason for withdrawal from the study will be recorded on the Study Status data collection form. Subjects will be encouraged to complete the Early Termination Visit. The Early Termination Visit procedures are listed in Section 7.7. Although subjects are free to withdraw at any time or may be withdrawn by the site PI or appropriate SI at any time, subjects who receive at least one dose of study vaccine will be encouraged to remain in the study for follow-up safety assessments and – in cohort 2 - collection of venous blood samples for immunogenicity testing. Every attempt will be made to follow all AEs, including solicited injection site and systemic reactions, SAEs, ongoing at the time of early withdrawal to resolution.

In the case of subjects who fail to appear for a follow-up safety assessment, extensive effort (i.e., three documented contact attempts via e.g. phone calls, e-mails, etc., made on separate occasions and followed by a certified letter, as applicable per local law) will be made to locate or recall them, or at least to determine their health status. These efforts will be documented in the subjects' records. See the protocol-specific manual for alternate follow-up requirements.

Subjects who withdraw, or are withdrawn or terminated from the study, or are lost to follow-up after signing the ICF, randomization, and receipt of study vaccine will not be replaced. Subjects who withdraw, or are withdrawn or terminated from the study, or are lost to follow-up after signing the ICF and randomization but before receipt of study vaccine may be replaced.

Subjects who do not receive second vaccination dose but have not withdrawn the consent for participation in the study are allowed to remain in the study upon PI's decision.

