7.7. Early Termination Visit

The following activities will be performed at the early termination visit for subjects who withdraw, or are withdrawn or terminated from the study:

- Obtain interim medical history by interview of subjects and note any changes since the previous visit.
- Memory aid information will be reviewed with subjects (if within 22 days after the last study vaccination, day of the vaccination inclusive).
- If indicated by medical history, perform physical examination and/or obtain vital signs including oral temperature. Subjects must not eat or drink anything hot or cold, or smoke within 10 minutes prior to taking oral temperature.
- Review and record all concomitant medications (if within 22 days after the last study vaccination, day of the vaccination inclusive).
- Information regarding reactions recorded in diary/-ies, AEs and SAEs will be recorded on the appropriate data collection form. Recording of AEs in the EDC will be limited to SAEs if after 21 days following the last study vaccination day.

- Examine study vaccination site, and perform post- administration reactogenicity assessment (if within 8 days after the last study vaccination, day of the vaccination inclusive).

7.8. **Unscheduled Visit**

Unscheduled visits may occur at any time during the study. Any of the following activities may be performed:

- Review memory aid (if within 22 days after the last study vaccination day, inclusive of the vaccination day).
- Review and record all concomitant medications (if within 22 days after the last study vaccination day, inclusive of the vaccination day).
- All reactions recorded in diary/-ies, AEs, SAEs will be recorded on the appropriate data collection form. Recording of AEs in the EDC will be limited to SAEs if after 21 days after the last study vaccination day.
- Obtain interim medical history by interview of subjects and note any changes since the previous visit (if indicated).
- If deemed as relevant and/or needed, perform physical examination and/or obtain vital signs including oral temperature. Subjects must not eat or drink anything hot or cold, or smoke within 10 minutes prior to taking oral temperature.
- Examine study vaccination site and perform post- administration reactogenicity assessment (if within 8 days after the last study vaccination, inclusive of vaccination day).

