#### Protocol-defined Influenza-Like Illness (ILI)

An ILI episode was identified if at least one respiratory symptom and at least one systemic symptom occurred concurrently; the respiratory symptoms being either

- sore throat,
- cough,

- sputum production,
- nasal discharge or congestion,
- wheezing or difficult breathing

and the systemic symptoms being either

- fever (oral temperature  $>37.2^{\circ}\text{C}$  for age 50-59 years, or  $>36.7^{\circ}\text{C}$  for age 60 years or more, or increased  $\geq 1.3^{\circ}\text{C}$  from baseline),
- headache,
- myalgia and/or arthralgia,
- chills,
- fatigue (tiredness for at least 12 hours).

The time of onset for an ILI episode is defined as the time from 14 days after the second vaccination to the date when at least one respiratory symptom and at least one systemic symptom occurred concurrently. For subjects who received only one vaccination, the time of onset for the ILI episode will be defined from 35 days after first vaccination. New episodes of ILI are defined as occurring at least 14 days after the end of a previous episode.

The duration of the ILI episode (days) is defined as follows: last stop date of ILI symptoms for the episode - onset date of the ILI episode + 1.

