## 5.2 Efficacy Assessment

The assessment of vaccine efficacy will be performed over one flu season and will focus on events which occurred during the flu season in cohorts 1 and 2. Given the surveillance plan, only events which occurred at least 14 days after the second vaccination will be captured.

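### Losing eligibility after dosing may end study follow-up, and one-dose subjects, who count in ITT, have no defined swabbing period

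*Protocol*

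**What the plan says.** Protocol 5.3.3 has two lists. The first begins "A subject may withdraw or be withdrawn from the study for any of the following reasons"; the second governs withholding further vaccination. "Subject no longer meets eligibility criteria" stands in both, and neither the entry nor its list is limited to the period before the first dose. Among the criteria a subject could cease to meet is exclusion 4 in 5.2: "Any serious disease such as: cancer, autoimmune disease, advanced arteriosclerotic disease or complicated diabetes mellitus".

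Protocol 5.3.4 says "Subjects who do not receive second vaccination dose but have not withdrawn the consent for participation in the study are allowed to remain", but makes this the investigator's decision. It encourages anyone with at least one dose to stay for safety assessments and, in Cohort 2, blood sampling. Influenza surveillance is not mentioned. It also promises to follow adverse events ongoing at withdrawal until they resolve.

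Protocol 7.3 starts passive reporting and swab collection 14 days after the second vaccination. Active calls run by calendar date. SAP 5.1 says that for subjects with a single dose the "time of onset for the ILI episode will be defined from 35 days after first vaccination". SAP 5.2 says "only events which occurred at least 14 days after the second vaccination will be captured".

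For the early termination visit, Protocol 7.7 states: "Recording of AEs in the EDC will be limited to SAEs if after 21 days following the last study vaccination day". Section 7.8 sets the same limit for unscheduled visits.

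**The concern.** Stopping vaccination and ending observation are different decisions. Elsewhere the protocol keeps them apart: pregnant subjects receive no further doses but stay in safety follow-up (9.3.2), and vaccinated subjects are still followed if the trial is discontinued (14.6). Section 5.3.3 does not keep them apart for loss of eligibility.

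Two things are at stake. First, 3.2.1 makes NOCIs and all SAEs, whatever their cause, primary safety outcomes up to the end of the first passive surveillance period. A reason for leaving that can itself be one of those outcomes makes the remaining follow-up depend on the outcome. Second, the VE estimate has no follow-up time in it, so an unobserved case becomes a non-case. One-dose subjects are the group most exposed to this. They include people stopped because of a grade 3 reaction with no other explanation, which is also a primary safety outcome.

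**Working it through.** **1. The plan's own figure.** Inputs from Protocol 11.3.2: VE bound 40%, true VE 62%, two-sided 95% interval, 182 events, 1:1 allocation. With q = RR/(1+RR), q0 = 0.6/1.6 = 0.375 and q1 = 0.38/1.38 = 0.2754. Under the exact conditional binomial, success with 182 events needs at most 55 M-001 cases, and exact power is 81.5% against the stated 80%. Reading 2.41% as the placebo attack rate, expected events are 12,000 × 0.9/2 × 0.0241 × 1.38 = 179.6. The design figure reproduces.

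**2. Where eligibility and safety outcomes overlap.** A serious disease first diagnosed after dosing can breach exclusion 4 (5.2), can be a NOCI or SAE (9.2.1, 9.2.4), and is then a reason the subject may be withdrawn (5.3.3). Events ongoing at that moment are followed (5.3.4). For later ones, 9.3 says SAEs after early termination need not be reported unless the investigator suspects the product or a procedure, whereas 3.2.1 counts SAEs regardless of relatedness.

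**3. Who is in which denominator.**
- ITT: everyone with at least one dose (Protocol 11.5.1, SAP 5.3), so one-dose subjects are included.
- PP (primary): both doses required. One surveillance contact 15 days or more after dose 2 is enough, so a two-dose subject withdrawn later stays in N.
- VE = 1 − (C_V/N_V)/(C_P/N_P) in both sets, with no imputation (11.5.4).

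**4. Effect on ITT VE (illustration).** The documents give no missed-dose rate and no one-dose VE. Assume two-dose VE 62% (RR 0.38), one-dose VE 0 (RR 1), and a fraction m missing dose 2. In units of the placebo attack rate:
- full capture: M-001 = (1−m_V)×0.38 + m_V; placebo = 1
- no one-dose capture: M-001 = (1−m_V)×0.38; placebo = 1−m_P

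| Missed dose 2, M-001 / placebo | Full capture: M-001, VE | No one-dose capture: M-001, placebo, VE | VE overstated by |
|---|---|---|---|
| 2% / 2% | 0.3924, 60.8% | 0.3724, 0.98, 62.0% | 1.2 points |
| 5% / 5% | 0.4110, 58.9% | 0.3610, 0.95, 62.0% | 3.1 points |
| 4% / 2% | 0.4048, 59.5% | 0.3648, 0.98, 62.8% | 3.3 points |

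With equal rates the placebo attack rate is understated by 2-5%, and the M-001 rate by 0.02/0.3924 = 5.1% to 0.05/0.4110 = 12.2%. The arms are not understated equally, which is why VE moves. One-dose VE of 0 is the unfavourable end. At one-dose VE 62%, equal rates give no distortion, and the 4%/2% split gives 1 − (0.96×0.38)/0.98 = 62.8% against 62.0%, or 0.8 points.

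**5. Scale for PP (illustration).** Suppose a share d more M-001 than placebo cases goes unseen because two-dose subjects left. A true VE of 40% then appears as 1 − 0.6(1−d): 40.6%, 41.2% and 43.0% for d = 1%, 2% and 5%. One-sided type I error at 182 events rises from 2.4% to 2.8%, 3.3% and 5.0%. Nothing in the documents says that such a difference would arise, or in which direction.

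**6. NOCI recording.** Sections 7.3, 9.2.1 and 9.3 require NOCIs throughout participation, and 7.4 asks for them at Day 202. Section 7.7 restricts late recording to SAEs. These conflict.

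**The case against.** The case against is substantial, and most of it limits the size of the point.

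- Withdrawal is permissive, and 5.3.4 works against it through encouragement to stay, follow-up of ongoing events, and repeated contact attempts for missed safety assessments. This stands. It does not reach new events or influenza surveillance.
- A reader might infer from 7.7 that a non-serious NOCI prompting withdrawal is lost. The documents do not support that: such a NOCI arises during participation, where 7.3, 9.2.1 and 9.3 require it, and SAP 4.4 tabulates NOCIs up to 30 days after discontinuation. What remains is a contradiction to reconcile.
- A reader might infer that influenza itself removes subjects. It does not. The acute-illness exclusion concerns the week before the first dose, eligibility is scheduled for review only at Visits 1 and 2, and a first confirmed episode has already been counted if the subject leaves afterwards.
- A reader might infer that one-dose subjects bias the primary decision. They cannot, because PP requires both doses.
- The 4%/2% split has no source. Protocol 2.3.1 reports adverse events similar to placebo, and assessors are blinded.
- No one-dose capture at all is a worst case: active calls are calendar-based and SAP 5.1 plainly expects one-dose episodes. But 7.3 still ties swabs to dose 2, and an unswabbed illness cannot be a confirmed case.
- Protocol 11.5.3 calls for a Cox model if discontinuation differs by arm, and SAP 5.4.2 censors at last contact. That answers the missing follow-up time, but not withdrawal related to outcome.

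**Conclusion.** The point holds in a limited form. For safety the link is direct: a primary safety outcome can be the stated reason for leaving, and events that begin afterwards are only partly covered. For efficacy it is indirect. The one-dose part affects supportive ITT and safety only, with ITT VE overstated by about 1-3 points under equal missed-dose rates of 2-5%, one-dose VE of 0 and no one-dose capture, and by less if either of the last two assumptions is relaxed. The primary PP analysis is exposed only through two-dose subjects withdrawn after a qualifying contact; the documents give neither their number nor any reason to expect imbalance between arms. SAP 5.1 and 5.2 contradict each other on one-dose events, and 7.7 contradicts 7.3, 7.4, 9.2.1 and 9.3 on NOCIs, whatever the rates turn out to be. No view is taken on when vaccination should be withheld.

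**What to change.** 1. Protocol 5.3.3: delete the loss-of-eligibility entry from the study-withdrawal list only. Leave the dose-2 list and the investigator's safety reason as they are.
2. Protocol 5.3.4: state that subjects who miss dose 2 stay in ILI surveillance and safety follow-up to the end of passive surveillance, unless they withdraw consent or the retained safety reason applies. The second exception is needed so that the sentence does not contradict 5.3.3.
3. Protocol 7.3: define surveillance and swabbing for one-dose subjects from the start point already in SAP 5.1, and correct the SAP 5.2 sentence to match.
4. Protocol 7.7, and the parallel line in 7.8: extend the late-recording restriction to SAEs and NOCIs, so that it agrees with 7.3, 7.4, 9.2.1 and 9.3.

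The calls, swabs and forms already exist. The cost is a protocol amendment, with the regulatory and ethics submissions that 14.2 requires, and a few more subjects kept under surveillance. It can apply to Cohort 2 only, because Cohort 1 participation ended with Season 1 (7.5).

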5.3.4. Handling of Withdrawals

The primary reason for withdrawal from the study will be recorded on the Study Status data collection form. Subjects will be encouraged to complete the Early Termination Visit. The Early Termination Visit procedures are listed in Section 7.7. Although subjects are free to withdraw at any time or may be withdrawn by the site PI or appropriate SI at any time, subjects who receive at least one dose of study vaccine will be encouraged to remain in the study for follow-up safety assessments and – in cohort 2 - collection of venous blood samples for immunogenicity testing. Every attempt will be made to follow all AEs, including solicited injection site and systemic reactions, SAEs, ongoing at the time of early withdrawal to resolution.

In the case of subjects who fail to appear for a follow-up safety assessment, extensive effort (i.e., three documented contact attempts via e.g. phone calls, e-mails, etc., made on separate occasions and followed by a certified letter, as applicable per local law) will be made to locate or recall them, or at least to determine their health status. These efforts will be documented in the subjects' records. See the protocol-specific manual for alternate follow-up requirements.

Subjects who withdraw, or are withdrawn or terminated from the study, or are lost to follow-up after signing the ICF, randomization, and receipt of study vaccine will not be replaced. Subjects who withdraw, or are withdrawn or terminated from the study, or are lost to follow-up after signing the ICF and randomization but before receipt of study vaccine may be replaced.

Subjects who do not receive second vaccination dose but have not withdrawn the consent for participation in the study are allowed to remain in the study upon PI's decision.

